### 10. STUDY DRUG MATERIALS AND MANAGEMENT

### 10.1. Study Drug

Capsules containing either RTA 408, in the 2.5-mg and 10-mg or 50-mg strengths, or the corresponding placebos, as described in Table 7, will be used in this study.

Description	RTA 408 Capsule, 2.5 mg, 10 mg, 50 mg	Placebo Capsules
Ingredients	RTA 408, silicified microcrystalline cellulose, pregelatinized starch, croscarmellose sodium, magnesium stearate, in white opaque, size #4 or #0 capsule shells consisting of hypromellose and titanium dioxide	Silicified microcrystalline cellulose, pregelatinized starch, magnesium stearate, in white opaque, size #4 or #0 capsule shells consisting of hypromellose and titanium dioxide
Manufacturer		

Table 7: Study Drug Information

# 10.2. Study Drug Packaging and Labeling

RTA 408 active and placebo capsules are contained in identical primary container closure systems (i.e., 75-cc high-density polyethylene [HDPE] bottles with a foil induction-seal liner and a child-resistant closure). Treatment kits containing either three or four bottles, depending on treatment assignment will be provided to patients for self-administration. Each bottle will contain 30 capsules and a desiccant insert that must not be ingested. The label on each bottle will include the following information:

- Protocol 408-C-1403
- Medication ID number
- Caution statement: New Drug Limited by Federal Law to Investigational Use (United States [US]); For Clinical Trial Use Only (Non-US countries)
- Storage: Controlled room temperature, 20°C to 25°C (68°F to 77°F in the US), with excursions allowed between 15°C and 30°C (59°F to 86°F in the US)
- Sponsor name, address, and contact information
- Contents: One bottle containing 30 capsules of either RTA 408 or placebo. Bottle also contains one desiccant insert, which should not be ingested
- Directions for use: Take capsule as directed, orally, once daily in the morning on an empty stomach (1 hour before or 2 hours after eating) with water
- Keep out of sight and reach of children

- FOR ORAL USE ONLY
- Lot number (Non-US countries)
- Expiration date (Non-US countries)
- Study contact (Non-US countries)
- EudraCT number: 2014-003501-15 (European Union countries)

Additionally, expiry information will be provided on treatment kits intended for use in the EU.

# **10.3.** Study Drug Storage

The stability of the drug product is being evaluated in ongoing studies.

Investigative sites must store the investigational product in a secure location under controlled room temperature conditions of 20°C to 25°C (68°F to 77°F), with excursions allowed between 15°C and 30°C (59°F to 86°F). Sites must maintain documentation of appropriate storage conditions. If a temperature within the storage location at the site is noted to be outside the excursion range for 24 hours or more or exceeds 40°C, the Sponsor must be notified.

# **10.4.** Study Drug Administration

Please refer to Section 9.9.21 for details on study drug administration. Patients will receive enough capsules for continuous dosing once daily at least until the next study visit. Clear instructions will be provided to the patient regarding study drug administration for each study drug administration time point listed in Table 3.

# **10.5.** Study Drug Accountability

The investigator or designee will maintain a record of all study drug received, dispensed, and returned to the Sponsor or its designee. No study drug shall be destroyed by the clinical site unless directed to do so by the Sponsor or its designee. Study drug bottles and any unused capsules should be returned by the patient to the study staff.

# 10.6. Study Drug Handling and Disposal

The Sponsor or its designee will direct the site regarding the final disposition of any remaining study drug.

# 11. EFFICACY ASSESSMENTS

### **11.1. Maximal Exercise Test**

The following parameters will be collected during the maximal exercise test and analyzed from Baseline to Weeks 4 and 12: change in peak work, peak oxygen utilization, and cardiac output at selected sites.

### **11.2.** Submaximal Exercise Test

The following parameters will be collected during the submaximal exercise test and analyzed from Baseline to Weeks 4 and 12: change in peak serum lactate, change in peak serum pyruvate, change in peak heart rate, and change in the rating of perceived exertion.

# **11.3.** Six-Minute Walk Test

The change in 6MWT distance from Baseline to Weeks 4, 8, and 12 will be analyzed.

### **12.** SAFETY ASSESSMENTS

### **12.1.** Safety Parameters

Safety parameters include results of echocardiogram, ECG, vital sign measurements, weight, BMI, physical examination, AEs, SAEs, concomitant medications, and laboratory tests (clinical chemistry, hematology, urinalysis, microscopy, and pregnancy tests [as indicated]).

### 12.2. Adverse and Serious Adverse Events

#### 12.2.1. Definition of Adverse Events

#### 12.2.1.1. Adverse Event

An AE is defined as any untoward medical occurrence in a patient regardless of its causal relationship to study treatment. An AE can be any unfavorable and unintended sign (including any clinically significant abnormal laboratory test result), symptom, or disease temporally associated with the use of the study drug, whether or not it is considered to be study drug related. Included in this definition is any newly occurring event or previous condition that has increased in severity or frequency since the administration of study drug.

All AEs that are observed or reported by the patient during the study (from the time of the first dose of study drug until the final visit or 30 days following final study dose for patients who terminate early) must be reported, regardless of their relationship to study drug or their clinical significance.

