#### Table 3:Overall Schedule of Assessments

a These procedures should be performed for early termination.

b Screening procedures for each patient should occur over the course of a few days and must finish at least 1 day prior to randomization. Study Day -1 is the day prior to first dose of study drug.

- c All Day 1 procedures should be performed prior to administration of first dose of study drug.
- d Assessments for Visit 3 may be collected at a home health nurse visit (at appropriate locations and approved by Sponsor) or at the study center clinic.
- e Assessments for Visit 4 must be collected at the study center if patients are enrolled in Part 1 of the study. If patients are enrolled in Part 2 of the study, Visit 4 assessments may be collected by a home health nurse.
- f Visit 6 should be conducted within 18 hours to 48 hours of Visit 5, and Visit 11 should be conducted within 18 hours to 48 hours of Visit 10.
- g For patients with echocardiograms and electrocardiograms collected within 30 days prior to the Screening Visit, the most recent echocardiogram and electrocardiogram can be used to assess cardiac function and patient eligibility.
- h At Week 2, electrocardiogram is only required for patients in Part 1 of the study.
- i A home health nurse visit may be used to collect all lab samples required at the Screening Visit.
- j Patients must be allowed to rest for a minimum period of 1 hour following maximal or submaximal exercise testing before this blood sample is collected (at the same time as all of the central lab blood collection). This sample must be taken prior to the 6MWT. This sample should be taken with the patient in the same position (e.g., sitting or semi-recumbent) at all appropriate visits
- k Blood samples will be collected to analyze for hepatitis B and C and HIV antibodies only in patients lacking evidence of a negative titer in the past year.
- Negative serum pregnancy test results are required at the Screening Visit before study enrollment, and negative urine pregnancy test results are required at all other times indicated for continued participation in the study.
- m At Week 2, study drug dispensation is only required for patients in the first cohort of Part 1 of the study.
- n A dosing diary check must be performed at study drug return and pill count.

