- o At Week 2, study drug return, pill count, and diary check are only required for patients in the first cohort of Part 1 of the study.
- p Study drug should be administered in the presence of study staff in the clinic on Day 1 after all Day 1 assessments have been completed. Study drug should also be administered in the clinic on Days 14, 28 (Part 2 only), 56 (Cohort 1; Part 1 only) and 84 after the blood collection for predose PK analysis. All other doses can be administered at home. RTA 408 should be administered once daily through Day 84.
- q On study days where multiple assessments are to be completed, the maximal exercise test will be the first functional assessment performed. Blood samples will be collected at rest, at the completion of the test, and at 5 and 10 minutes after the test. Maximal exercise testing should be repeated prior to randomization if the original Screening assessment was performed >30 days prior to Day 1.
- r As part of the submaximal exercise test, blood samples will be collected at rest and at 10-minute intervals throughout the test.
- s Muscle needle biopsy, which is optional, should be collected after all study visit assessments are performed, except on Day 1, in which muscle needle biopsy should be the second to last procedure performed, collected prior to study drug administration.
- t For patients enrolled in the first cohort of Part 1 of the study, blood samples for PK analysis at Visit 4 and Visit 8 should be collected prior to study drug administration as well as 1, 2, 4, and 8 hours after study drug administration. A single blood sample for PK analysis at Visit 11 should be collected prior to study drug administration.
- u For patients enrolled in the second and subsequent cohorts of Part 1 of the study, blood samples for PK analysis at Visit 4 should be collected prior to study drug administration as well as 1, 2, 4, and 8 hours after study drug administration. A single blood sample for PK analysis at Visit 11 should be collected prior to study drug administration.
- v For patients enrolled in Part 2 of the study, blood samples for PK analysis at Visit 6 and Visit 11 should be collected prior to study drug administration.
- w Blood collection for biomarkers will be optional. On Day 1, blood collection for blood biomarkers must occur prior to study drug administration.

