### 9.9.1. Informed Consent

Written informed consent (Section 17.3) must be obtained from the patient before any study-related procedures are performed, and if there is a change in the study procedures that could affect the patient's willingness to participate.

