#### 12.2.1.2. Serious Adverse Event

An SAE is any AE occurring at any dose and regardless of causality that:

- Results in death
- Is life-threatening
- Requires inpatient hospitalization or prolongation of existing hospitalization
- Results in persistent or significant incapacity or substantial disruption of the ability to conduct normal life functions
- Is a congenital anomaly or birth defect in an offspring of a patient taking study drug
- Is an important medical event

The term "life-threatening" refers to an event in which the patient was at immediate risk of death at the time of the event. It does not refer to an event that hypothetically might have caused death if it were more severe.

Important medical events are those that may not meet any of the criteria defined above; however, they may be considered serious when, based upon appropriate medical judgment, they may jeopardize the patient and may require medical or surgical intervention to prevent one of the other outcomes listed in the SAE definition.

Pregnancy is not considered an AE; however, information will be collected for any pregnancies that occur during the study (from the time of first dose of study drug until the final visit). Certain pregnancy outcomes will require submission as an SAE (Section 9.7.3).

The investigator is responsible for reporting to the Sponsor or its designee all AEs and SAEs that are observed or reported by the patient during the study (from the time of first dose of study drug until the final visit), regardless of their relationship to study drug or their clinical significance. All SAEs reported or observed during the study must be followed to resolution or until the investigator deems the event to be chronic or the patient to be stable. The Sponsor or its designee may contact the investigator to obtain additional information on any SAE that has not resolved at the time the patient completes the study.

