# 12.6. Recording Adverse Events

All conditions present prior to the first dose of study drug should be documented as medical history. All drug-related (characterized as possibly or probably related; Section 12.4) AEs and abnormal laboratory test results reported or observed during the study must be followed to resolution (either return to baseline or within normal limits). All other AEs or non-drug-related abnormal laboratory results will be followed through the final visit (i.e., end of study or early termination). Information to be collected includes type of event, date of onset, date of resolution, investigator-specified assessment of severity and relationship to study drug, seriousness, as well as any action taken.

While an AE is ongoing, changes in the severity (e.g., worsening or improving) should be noted in the source documents but when documenting the AE, only the total duration and greatest severity should be recorded in the CRF. AEs characterized as intermittent require documentation of onset and duration.

AEs resulting from concurrent illnesses, reactions to concurrent illnesses, reactions to concurrent medications, or progression of disease states must also be reported. Pre-existing conditions (present before the start of the AE collection period) are considered concurrent medical conditions and should NOT be recorded as AEs. However, if the patient experiences a worsening or complication of such a concurrent condition, the worsening or complication (except disease progression) should be recorded as an AE. Investigators should ensure that the AE term recorded captures the change in the condition (e.g., "worsening of...").

Each AE should be recorded to represent a single diagnosis. Accompanying signs (including abnormal laboratory test values or ECG findings) or symptoms should NOT be recorded as additional AEs. If a diagnosis is unknown, sign(s) or symptom(s) should be recorded as an AE(s). Changes in laboratory test values or ECG parameters are only considered to be AEs if they are judged to be clinically significant (i.e., if some action or intervention is required or if the investigator judges the change to be beyond the range of normal physiological fluctuation). If abnormal laboratory test values or ECG findings are the result of pathology for which there is an overall diagnosis (e.g., increased creatinine levels in renal failure), only the diagnosis should be reported as an AE.

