## 7.1.2 Treatment-Emergent Adverse Events

Treatment-emergent AEs (TEAEs) are defined as any AEs, regardless of relationship to study drug, that have an onset or worsen in severity on or after the first dose of study drug. If it cannot be determined whether the AE is treatment-emergent due to a partial onset date, then it will be counted as a TEAE. Adverse events with incomplete start dates will be considered TEAEs, if:

- Onset time is missing but the onset date is on Study Day 1.
- Day and month are missing and the year is equal to or after the year of the first date of study drug dosing;
- Day is missing and the year is after the year of the first date of study drug dosing;
- Day is missing and the year is equal to the year of the first date of study drug dosing and the month is equal to or after the month of the first date of study drug dosing; or
- Year is missing.

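### AE and SAE reporting starts at the first dose, so complications of study procedures between consent and dosing need not be reported and have no defined route to the sponsor or DSMB

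*Protocol*

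**What the plan says.** Protocol 12.2.1.1 sets the reporting period for adverse events: "from the time of the first dose of study drug until the final visit", or 30 days after the last dose for patients who terminate early. Section 12.2.1.2 gives the investigator's duty to report AEs and SAEs to the sponsor the same start: "from the time of first dose of study drug until the final visit), regardless of their relationship to study drug". Section 12.6 covers what comes earlier: "All conditions present prior to the first dose of study drug should be documented as medical history". It adds that conditions pre-dating the collection period are not to be entered as AEs, except for a later worsening or complication.

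Consent comes well before that point. Under Protocol 9.9.1 it "must be obtained from the patient before any study-related procedures are performed". Table 3 then places these procedures ahead of dosing:

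- Screening includes the maximal exercise test and a 6MWT. The footnote reads: "Screening procedures for each patient should occur over the course of a few days and must finish at least 1 day prior to randomization".
- A second pre-dose maximal test is possible: "Maximal exercise testing should be repeated prior to randomization if the original Screening assessment was performed >30 days prior to Day 1".
- Footnote c puts every Day 1 procedure before the first dose. These include the 6MWT and, at the sites selected under 9.9.25, the submaximal test.
- For the optional biopsy on Day 1, "muscle needle biopsy should be the second to last procedure performed, collected prior to study drug administration".

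The AE-collection row of Table 3 is blank at Screening and marked at Day 1.

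**The concern.** The protocol asks exercise-intolerant patients to exercise to their maximum before any reporting duty begins. Its own text treats exertion here with care. Inclusion criterion 1a describes modest exercise provoking weakness or tachycardia. Appendix 2 lists a defibrillator among the equipment for the milder walk test and warns of arrhythmia or cardiovascular collapse in patients with the listed risk factors. The supplied text does not require the Screening echocardiogram, which supports some of the cardiac exclusions, to precede the Screening maximal test; the exercise manual was not available. Some patients tested at Screening may later prove ineligible.

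A syncope or arrhythmia during that test which resolves before dosing is, under 12.6, at most a medical-history entry. The 24-hour clock in 12.7 runs for AEs that meet the seriousness criteria, and 12.6 says pre-dose conditions are not AEs. At stake is whether the people overseeing safety reliably learn of harm caused by the study's own procedures in time to act for later patients.

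**Working it through.** The plan gives no figure to reproduce. The check sets the reporting window against the schedule, then looks for another route that closes the gap.

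**Step 1: procedures outside the window, per completing patient.** Counted from Table 3, without the conditional repeat:

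| Procedure | Before first dose | After first dose | Share before |
|---|---|---|---|
| Maximal exercise test | Screening | Weeks 4, 12 | 1 of 3 |
| 6MWT | Screening, Day 1 | Weeks 4, 8, 12 | 2 of 5 |
| Submaximal test (selected sites) | Day 1 | Weeks 4, 12 | 1 of 3 |
| Muscle biopsy (optional) | Day 1 | Week 12 | 1 of 2 |

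With the repeat maximal test the first row becomes 2 of 4.

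**Step 2: patients affected.** Part 1 has about 8 cohorts of 8: 8 × 8 = 64 (also in SAP 1.3). Part 2 has 24, or 36 after expansion. Totals: 64 + 24 = 88 and 64 + 36 = 100. Each has at least one pre-dose maximal test. Screen failures who were tested come on top; the documents give no number for them.

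**Step 3: other routes.**

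- Protocol 12.3 requires a health question at every visit, including hospitalizations and accidents. The answers go to source documents; no rule sends pre-dose answers to the sponsor.
- Medical history is recorded (12.6) and summarized and listed (SAP 4.4). It is absent from the safety parameters in Protocol 12.1 and 14.2.4 and in SAP 2.3.2, and has no expedited reporting.
- A post-dose worsening or complication is an AE (12.6). An event that resolves before dosing is not covered.
- Protocol 17.5 obliges the investigator to tell the IRB about risks to patients. That route goes to the IRB, and 17.5 sets out no passage to the DSMB.
- Protocol 7.5 and 12.7 give the DSMB a broad safety remit but do not say how a pre-dose event would get to it.
- The safety population needs at least one dose (Protocol 14.3.1, SAP 3.2.2), which leaves out screen failures. SAP 7.1.1 limits AE summaries to treatment-emergent events.

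None of these requires a pre-dose procedural SAE to be reported to the sponsor or passed to the DSMB.

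**Step 4: internal consistency.** Table 3 marks AE collection on Day 1, and footnote c places all Day 1 procedures before dosing. Read literally, AEs are collected at a point when 12.2.1.1 and 12.6 say there are none to record. The two must be reconciled.

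**The case against.** The best defence is that anchoring AEs to drug exposure is a legitimate and mostly consistent design choice, and that pre-dose events are not invisible. They are documented as medical history, asked about at visits, open to IRB notification, and entered in an EDC system that covers everyone who signed consent (Protocol 18.2). The DSMB's remit covers safety data in general, with no stated exclusion of pre-dose data. Complications of the Week 4 and Week 12 repeats of these procedures, and of the Week 8 walk test, fall inside the window. All of that stands. It shows that such events may be written down somewhere; it does not show that anyone must report them.

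Three stronger readings are tempting, and the documents do not support them.

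- A reader might infer that these events are never reported or never seen by the DSMB. The DSMB charter is a separate document that was not available, so what the board receives cannot be settled here.
- A reader might infer that SAP 7.1.2 distorts the treatment-emergent counts, because it includes an event when "Onset time is missing but the onset date is on Study Day 1". That rule serves events whose timing cannot be determined, and it errs toward counting them. A complication known to follow a pre-dose procedure belongs in medical history under 12.6 whether or not a clock time was written. One event in a dose group of 6 is 1/6, or 16.7 percentage points, but nothing in the documents suggests such misfiling is likely.
- A reader might rank maximal exercise as the main non-drug hazard. The documents give no event rates to support a ranking, and the protocol excludes clinically significant cardiac disease and raised BNP.

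**Conclusion.** The point holds as a gap in required reporting. Between consent and first dose, the protocol neither requires complications of its own procedures to be reported as AEs or SAEs nor defines how they reach the sponsor or DSMB. Every patient who reaches dosing is affected through the Screening maximal test and two walk tests; the submaximal test and biopsy add to this only where they are done.

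The figure of 88 to 100 patients assumes that all eight Part 1 cohorts are filled; Part 1 may stop sooner once doses are chosen. It counts cohort places, so screen failures are additional, although SAP 4.1 defines enrolment as signing consent. No complication rate is given, so the number of events missed cannot be estimated.

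The efficacy analysis is not affected, and no bias in the comparison of drug with placebo is shown. This is a patient-safety change that should be made because it is specific and cheap.

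**What to change.** Amend Protocol 12.2.1.1, 12.2.1.2, 12.6 and Table 3 so that SAEs, and AEs the investigator attributes to a protocol procedure, are collected and reported from signed consent to first dose, including in screen failures. Reconcile the Day 1 AE-collection mark and footnote c with that window, and carry the change into Tables 9 and 10 and SAP Table 1. The Day 1 query should cover the whole period since consent, and screen failures should be asked when the failure is recorded; a check at the Screening visit alone would miss events that arise afterwards.

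Show these events in a separate pre-treatment table supplied to the DSMB. Leave the treatment-emergent rule in SAP 7.1.2 as it is.

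The cost is a short amendment, a few more site reports and one extra table. Treatment and the efficacy analyses do not change.
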